This study will adapt and integrate a novel PrEP initiation intervention at point of care in rural SSPs using strengths-based case management (SBCM) approaches to elicit and address structural, environmental and psychosocial barriers to PrEP care. Participants will be randomized into: CDC-PrEP (an in-use PrEP intervention based on CDC guidelines), or the experimental SBCM-PrEP intervention. CDC-PrEP utilizes structured risk assessments and educational materials recommended by the CDC and operates as a point of care model with embedded APRNs providing clinical screening, prescribing, and monitoring of patients in a single session. SBCM-PrEP provides up to 5 strengths-based sessions to deliver tailored PrEP education and engage in action planning to increase readiness for PrEP initiation.

The rationale for the selection of the intervention comparators is threefold:

- 1) use of an active comparator (CDC-PrEP) meets an ethical standard to provide high-risk participants with needed basic education and the potential to access PrEP;
- 2) examination of a brief, in-use content specific intervention for PrEP based on CDC guidelines affords the opportunity to establish preliminary efficacy of an existing intervention that has not been formally tested within the SSP context, and whose brevity may contribute to scalability if efficacious; and
- 3) Comparison with the SBCM-PrEP will examine the value-added of a more robust, but brief, client-driven intervention that supports PrEP initiation through active advocacy to reduce multi-level barriers to uptake.

Objectives	7	Specific objectives or hypotheses
		
The primary objective is to examine preliminary efficacy and effect sizes of the novel SBCM-PrEP and CDC-PrEP interventions on the primary outcome of PrEP initiation (measured by dispensed PrEP prescription) in HIV- participants who inject drugs.

Trial design	8	
Description of trial design including type of trial (eg, parallel group, crossover, factorial, single group), allocation ratio, and framework (eg, superiority, equivalence, noninferiority, exploratory)
 
The trial is designed as a randomized, controlled exploratory trial with two parallel groups and a primary endpoint of PrEP initiation during 3 months after enrollment. Randomization will be stratified by site and gender and performed with a 1:1 allocation.

Methods: Participants, interventions, and outcomes

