	11b	Criteria for discontinuing or modifying allocated interventions for a given trial participant (eg, drug dose change in response to harms, participant request, or improving/worsening disease)

		-N/A
	11c	Strategies to improve adherence to intervention protocols, and any procedures for monitoring adherence (eg, drug tablet return, laboratory tests)
		Study staff will attempt to contact participants to remind them of intervention session appointments the day before each scheduled session, and participants will be allowed to reschedule missed sessions. In sessions participants will be asked about PrEP adherence, and problems or barriers addressed.
	11d	Relevant concomitant care and interventions that are permitted or prohibited during the trial
		N/A
Outcomes	12	Primary, secondary, and other outcomes, including the specific measurement variable (eg, systolic blood pressure), analysis metric (eg, change from baseline, final value, time to event), method of aggregation (eg, median, proportion), and time point for each outcome. Explanation of the clinical relevance of chosen efficacy and harm outcomes is strongly recommended
		Primary Outcome Measure: Difference between the two intervention arms in the number of participants initiating PrEP at 3 and 6 month follow-up.
		1. Number of participants initiating PrEP Documented PrEP initiation, measured by dispensed PrEP prescription. [Time Frame: 3 months post-baseline]
		2. Number of participants initiating PrEP Documented PrEP initiation, measured by dispensed PrEP prescription. [Time Frame: 6 months post-baseline]
		Secondary Outcome Measures:
		3. Level of Intervention Engagement assessed by session checklist 5 item Session Checklist completed by Nurse-Interventionist post-session; range is 0-15, higher scores are higher engagement

[Time Frame: 8 weeks post-baseline]

4. Level of Intervention Satisfaction assessed by the IAQ

8 item Intervention Acceptability Questionnaire (IAQ) completed by participants post-intervention; range is 0-32, higher scores are higher satisfaction

[Time Frame: 8 weeks post-baseline]

Participant timeline 13 Time schedule of enrolment, interventions (including any run-ins and washouts), assessments, and visits for participants. A schematic diagram is highly recommended (see Figure)

-Figure 1 and Table 1

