Sample size 14 Estimated number of participants needed to achieve study objectives and how it was determined, including clinical and statistical assumptions supporting any sample size calculations

The pilot RCT is not designed to establish superiority of the SBCM-PREP, but to generate valid parameter estimates and preliminary evidence of effect sizes for application in a subsequent large trial. The proposed sample size of 80 aligns with recommended sample sizes for two-arm pilot trials structured as planning for subsequent major trials. Assuming a retention rate of 90% at 6 months, there will be 36 participants per intervention group for analysis, which is sufficient.

Recruitment 15 Strategies for achieving adequate participant enrolment to reach target sample size

Recruitment is balanced across the two SSP locations and by gender, targeting enrollment of 40 individuals per location, or 80 in total. Within the SSP settings, potential participants will be screened by research staff on rotating days of the week when the SSPs are operational and eligible participants will be invited to participate. Approximately 6-8 individuals will be enrolled into the study each month across the two sites; challenges meeting the enrollment target based on prior research in these settings and current volumes of SSP clients are not anticipated.

Methods: Assignment of interventions (for controlled trials)

Allocation:

Sequence generation 16a Method of generating the allocation sequence (eg, computer-generated random numbers), and list of any factors for stratification. To reduce predictability of a random sequence, details of any planned restriction (eg, blocking) should be provided in a separate document that is unavailable to those who enroll participants or assign

interventions

Participants will be randomly assigned to either the CDC-PrEP or SBCM-PrEP with a 1:1 allocation per a computer-generated randomization schedule stratified by site and gender.

Allocation concealment mechanism	16b	Mechanism of implementing the allocation sequence (eg, central telephone; sequentially numbered, opaque, sealed envelopes), describing any steps to conceal the sequence until interventions are assigned -The study coordinator and PI are notified of the allocation via secure email.

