Statistical methods	
20a Statistical methods for analysing primary and secondary outcomes. Reference to where other details of the statistical analysis plan can be found, if not in the protocol
 
A total of 80 HIV- rural PWID will be randomly assigned to the two intervention groups. The major interest in Specific Aim 3 is to evaluate the preliminary efficacy of the intervention conditions on PrEP initiation (measured by dispensed PrEP prescription) at 3- and 6-month follow-ups. With 36 participants per intervention condition, and utilizing a 95% confidence interval, we will be able to estimate the true probability of PrEP initiation for either trial arm within a maximum of ± 0.16. To address Aim 3, robust analytic methods will be used for descriptive purposes and data analyses. Descriptive statistics (e.g., frequencies, proportions, means, and standard deviations) will be used to describe process variables (e.g., the number of sessions attended, engagement scores). Bivariable analyses will be used to examine potential differences in feasibility and acceptability between the two study conditions. Conventional statistical methods, such as t-tests, Chi- square, ANOVA, ANCOVA, OLS, and logistic regression will be used for preliminary analyses of the demographic and risk environment characteristics of PWID, as well as those associated with PrEP initiation. Tests will be two-sided at the 0.05 level. Similarly, to examine initiation of PrEP, as well as continuation of PrEP among those who initiated by 3 months, we will utilize frequencies, proportions, and corresponding 95% confidence intervals. Additionally, logistic regression models will be utilized to assess for group differences, adjusting for site due to its use as a stratification factor.
 
20b Methods for any additional analyses (eg, subgroup and adjusted analyses)
 
N/A
 
20c Definition of analysis population relating to protocol non-adherence (eg, as randomised analysis), and any statistical methods to handle

---------------------	---

missing data (eg, multiple imputation)

We will use an intent-to-treat approach, analyzing data from all participants based on the trial arms to which they were randomized regardless of whether they receive or complete the randomized treatment to which they were assigned.

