Aim 3 Analytic Plan and Sample Size Considerations. The overarching goal of this R34 is to adapt and feasibility test an evidence-based SBCM intervention, and examine preliminary efficacy of the intervention comparators (SBCM-PrEP and CDC-PrEP). Within this context, our Aim 3 pilot RCT is not designed to establish superiority of the SBCM-PrEP, but to evaluate feasibility of our procedures and implementation processes, examine acceptability of methods, intervention content and format, to generate valid parameter estimates and preliminary evidence of effect sizes for application in a subsequent R01, which are preferred endpoints for many pilot trials. The proposed sample size of 80 aligns with rules of thumb and recommended sample sizes for two-arm pilot trials structured as planning for subsequent major trials. Assuming a retention rate of 90% at 6 months, there will be 36 participants per intervention group for analysis, which is sufficient for the Aim 3 pilot.

Precision Analysis. A total of 80 HIV- rural PWID will be randomly assigned into the two intervention groups. The major interest related to Specific Aim 3 is to evaluate the preliminary efficacy of the intervention conditions on the primary study outcome (PrEP initiation, measured by dispensed PrEP prescription) at 3- and 6- month follow-ups. With 36 participants per intervention condition, and utilizing a 95% confidence interval, we will be able to estimate the true probability of PrEP initiation for either trial arm within a maximum of ± 0.16 .

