To address Aim 3, robust analytic methods will be used for descriptive purposes and data analyses. Descriptive statistics (e.g., frequencies, proportions, means, and standard deviations) will be used to describe targeted process variables (e.g., proportion of women agreeing to enroll in the study, the number of sessions attended, engagement scores, etc.). Bivariable analyses will be used to examine potential differences in feasibility and acceptability between the two study conditions. Conventional statistical methods, such as t-tests, Chi-square, ANOVA, ANCOVA, OLS, and logistic regression will be used for preliminary analyses of the demographic and risk environment characteristics of PWID, as well as those associated with PrEP initiation. Tests will be two-sided at the 0.05 level. Similarly, to examine initiation of PrEP, as well as continuation of PrEP among those who initiated by 3 months, we will utilize frequencies, proportions, and corresponding 95% confidence intervals. Additionally, logistic regression models will be utilized to assess for group differences, adjusting for site due to its use as a stratification factor.

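### The between-arm model adjusts for site as a stratification factor but leaves out gender, which also stratifies randomisation; the fix is to add gender, and secondarily to state precision for the between-arm difference

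*Combined protocol and SAP*

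**What the plan says.** **Randomisation.** Item 8 (Trial design): "Randomization will be stratified by site and gender and performed with a 1:1 allocation". Item 16a (Sequence generation) repeats this with a "computer-generated randomization schedule stratified by site and gender". Item 15 adds: "Recruitment is balanced across the two SSP locations and by gender".

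**Analysis model.** Item 20a and the last paragraph of the SAP carry the same sentence: "logistic regression models will be utilized to assess for group differences, adjusting for site due to its use as a stratification factor". Gender is not named. Item 20b, on subgroup and adjusted analyses, is marked not applicable.

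**Target and precision.** Item 7 seeks "preliminary efficacy and effect sizes of the novel SBCM-PrEP and CDC-PrEP interventions". Item 12 heads the primary outcome as "Difference between the two intervention arms in the number of participants initiating PrEP at 3 and 6 month follow-up". The only precision statement, in item 20a and the SAP's Precision Analysis, is that with 36 per arm the trial can "estimate the true probability of PrEP initiation for either trial arm within a maximum of" ±0.16.

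**Denominator.** Item 14 and the SAP reach 36 per arm by taking 90% retention at 6 months. Item 20c analyses everyone as randomised and expects withdrawals and loss to follow-up not to affect the primary outcome.

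**The concern.** The plan gives its own rule for choosing the covariate: site is in the model because it stratified the randomisation. Gender meets the same rule and is missing. Stratifying on a factor that predicts the outcome reduces chance imbalance and so the true variability of the arm comparison. A model without that factor does not credit the reduction, so its intervals can be too wide and its tests too cautious. With the covariate list unclear, the choice between two models could also be made after the data are in, and the trial is unblinded (item 17a).

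The second matter is smaller. The pilot is justified by precision rather than power, and it is meant to pass effect sizes to a later trial. A planner looking for the precision of the between-arm difference finds only the single-arm figure.

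**Working it through.** **1. The covariate rule, set side by side.** Stratification factors: site, gender (items 8 and 16a). Stated reason for adjustment: use as a stratification factor (item 20a, SAP). Factors meeting that reason: site, gender. Factors named: site.

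The same paragraphs also plan logistic regression on demographic characteristics associated with initiation. That is described as preliminary analysis and does not put gender in the arm comparison.

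**2. The plan's own precision figure.** Inputs: 80 randomised 1:1, 90% retention, 95% confidence; worst case p = 0.5.

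- Per arm: 80/2 × 0.90 = 36.
- Single arm: 1.96 × √(0.25/36) = 0.163. The stated ±0.16 reproduces.

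**3. The same calculation for the difference**, both arms at 0.5, unadjusted Wald:

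- 36 per arm: 1.96 × √(0.25/36 + 0.25/36) = 0.231.
- 40 per arm: 1.96 × √(0.25/40 + 0.25/40) = 0.219.

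The difference is √2 = 1.41 times less precise than one arm. These are upper bounds. At an assumed 20% against 40% with 36 per arm the half-width is 0.207.

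**4. Effect of leaving gender out.** The documents give no expected rates, so every rate here is an assumption. The simulation has 80 participants, 10 in each of the 8 arm × site × gender cells (two gender levels assumed), and no arm effect. The logistic model is fitted with site, or with site and gender. The risk difference is standardised from the model with a delta-method 95% interval. The first three rows use 20,000 replicates, the last three 4,000.

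| Initiation by gender | Mean half-width, site only | Mean half-width, with gender | True spread (1.96 × SD) | Coverage, site only / with gender | Type I error, site only / with gender |
|---|---|---|---|---|---|
| 70% / 30% | 0.216 | 0.195 | 0.201 | 96.2% / 93.9% | 3.8% / 5.0% |
| 60% / 30% | 0.214 | 0.203 | 0.209 | 95.5% / 94.1% | 4.4% / 4.9% |
| 50% / 50% | 0.215 | 0.214 | 0.219 | 94.5% / 94.4% | 5.5% / 5.5% |
| 40% / 30% | 0.205 | 0.203 | – | 94.9% / 94.4% | – |
| 30% / 20% | 0.186 | 0.183 | – | 94.8% / 94.4% | – |
| 25% / 15% | 0.171 | 0.169 | – | 94.8% / 94.1% | – |

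Where it was recorded, the true spread is the same for both models. With balanced cells, adding gender changes the reported interval and the test, not the variability of the estimated risk difference. The site-only interval is clearly too wide only when the gender gap is large.

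**5. Sparse events.** Take an assumed 10% initiation and 10 per cell. The chance that one cell has no initiators is q = 0.9^10 = 0.349, and one level of a factor covers four cells. By inclusion–exclusion, the chance that some level has no initiators is:

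- Arm and site: 4q⁴ − (4q⁶ + 2q⁸) + 4q⁸ − q⁸ = 0.052.
- Arm, site and gender: the same calculation over six levels gives 0.072.

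At an assumed 5% the figures are 0.346 and 0.422; at 20% both are below 0.001. Most of the sparse-event risk is already in the site-only model.

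**The case against.** The strongest case against is that the practical consequence is small. At gender gaps of 10 points the site-only model already covers at 94.8% to 94.9%, and the model with gender sits slightly lower, at 94.1% to 94.4%. At 60% against 30%, the site-only interval is about 0.006 too wide and the gender-adjusted one about 0.006 too narrow. All of that stands. The case for adding gender is consistency with the plan's own rule and protection if gender matters, not a guaranteed gain.

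It is also fair to say that no stated figure is wrong. The ±0.16 is correct and correctly labelled as a single-arm figure. It fits the objective in item 7, which can be read arm by arm, and the plan says the pilot is not designed to show superiority. The figure for the difference follows from it by a factor of √2. That makes the missing sentence a secondary matter.

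A reader might infer more than the documents support:

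- *That leaving out gender biases the comparison.* Randomisation protects the risk difference whether or not gender is in the model.
- *That 36 against 40 is an error, or that 80 is too few.* Using 36 is conservative. It is also defensible, because item 18a verifies dispensing partly from participants' own documentation, which may be missing for people lost to follow-up.
- *That the primary outcome is undefined when dispensing is not verified.* Item 12 requires documented initiation by a dispensed prescription and item 18a describes the verification, so counting an unverified prescription as not initiated is the natural reading. The reference in item 20c to a prescription being issued is loose wording.

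**Conclusion.** The inconsistency is real and appears in both item 20a and the SAP. Gender stratifies the randomisation, the reason given for including site covers it, and its absence is not explained. The result is a somewhat conservative analysis if gender strongly predicts initiation, and almost no difference otherwise. At an assumed 70% against 30%, the site-only half-width is 0.216 against a true spread of about 0.20, with type I error of about 3% to 4%; adding gender gives about 0.195 and 4% to 5%.

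These figures rest on assumed rates, exact balance across cells, two gender levels and no arm effect. The documents state no block size, so exact balance is a simplification.

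Secondarily, the between-arm difference has no stated precision although item 12 makes it the primary outcome. Its worst case is ±0.23 at 36 per arm, or ±0.22 if all 40 are analysed as item 20c implies. This is a gap in what is reported, not a sample-size fault.

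**What to change.** **Main change.** In item 20a and the matching SAP sentence, have the group-difference model adjust for site and gender, because both stratify the randomisation.

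**Secondary change.** In item 20a and the Precision Analysis, keep ±0.16 for a single arm and add one sentence: *the unadjusted between-arm difference will be estimated to within at most ±0.23 with 36 per arm (±0.22 if all 40 per arm are analysed).*

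**Optional wording.** In item 20c, align the reference to an issued prescription with the dispensed-prescription outcome of items 12 and 18a.

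**Cost.** Two sentences of text and one model term, using data already collected; N stays at 80. The extra term raises the chance that some level has no initiators from 5.2% to 7.2% at an assumed 10% initiation. If the risk difference is taken from the model with a delta-method interval, expect coverage of about 94%. A standardised risk difference, a penalised (Firth) model or a Newcombe interval for sparse data are reasonable choices for the team to consider, but the inconsistency does not require them.
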